16. DISSEMINATION POLICY

Data arising from the trial will be owned by King's College London. It is intended that the results of the study will be reported and disseminated at international conferences and in peer-reviewed scientific journals. Where appropriate, the results will be disseminated to the general public by means of press releases, posts on social media and at public engagement events. The Consort Guidelines and checklist will be reviewed prior to generating any publications for the trial. Individual participants will not be identifiable in publications.

17. INDEMNITY

Insurance and indemnity will be provided by King's College London policies.

18. FINANCIAL ASPECTS

[name] NIHR Senior Investigator Award, Activity Code: RE13018

The study drug and formulation will be provided by SEEK pharmaceuticals.

29. ARCHIVING

At the end of this trial, all trial data will be stored in line with the Medicines for Human Use (Clinical Trials) Amended Regulations 2006 and the 2018 Data Protection Act and archived in line with the Medicines for Human Use (Clinical Trials) Amended Regulations 2006 as defined in the Sponsor Archiving SOP.

20. AMENDMENT HISTORY

Amendment No.	Protocol version no.	Date issued	Author(s) of changes	Details of changes made
1	1.1	10/01/2022	[name]	MHRA recommended changes
1	1.2	07/03/2022	[name]	Non-substantial

## 1. Abbreviations

AE	Adverse Event
AR	Adverse Reaction
AUC t	Area under the plasma concentration-time curve from time zero to time t.
AUC inf	Area under the plasma concentration-time curve from time zero to time infinity.
Bioavailability	The proportion of drug absorbed into the systemic circulation
BP	Blood Pressure
C max	The maximum serum concentration that a drug achieves
C mean	The mean serum concentration that a drug achieves over a specified period of time
CBD	Cannabidiol
CRF	Clinical Research Facility
DEQ-5	Drug Effects Questionnaire
FAS	Full Analysis Set
GCP	Good Clinical Practice
GMP	Good Manufacturing Practice
GSRS	Gastrointestinal Symptom Rating Scale
HR	Heart Rate
King's CRF	NIHR Wellcome Kings Clinical Research Facility
KHPCTO	The King's Health Partners Clinical Trials Office
MHRA	Medicines and Healthcare products Regulatory Agency
NA	Not Applicable
PK	Pharmacokinetic
REC	Research Ethics Committee
RR	Respiratory Rate
PI	Principal Investigator
PPS	Per Protocol Set
SAE	Serious Adverse Event
SAP	Statistical Analysis Plan
SAR	Serious Adverse Drug Reactions
SLaM	South London and Maudsley NHS Foundation Trust
SUSAR	Suspected Unexpected Serious Adverse Reactions
Temp	Temperature
T max	The time after administration of a drug that the C max is observed
T ½	The time taken for the plasma concentration to fall by half its original value
UAR	Unexpected Adverse Reactions

## 2. Source Documents

The Statistical Analysis Plan (SAP) was written based on the following documentation:

Document	Date	Version
Protocol	1.2	07/MAR/2022
CRF	2.0	26/APR/2022

## 3. Trial Design

Single-centre double-blind two-period crossover pharmacokinetic study.

The study includes one baseline screening visit followed by two experimental visits each lasting 48 hours, separated by a minimum 2 weeks washout. Participants will return home each day and will not stay in the hospital overnight.

## 4. Primary objective

To assess whether the novel formulation is able to increase the bioavailability of oral CBD in the fasting state.

Hypothesis: the novel formulation will increase the  $AUC_{inf}$  for a single dose of oral CBD in the fasting state.

## 5. Primary outcome

Difference in  $AUC_{inf}$  for a single dose of oral CBD between the novel and standard formulations in the fasting state.

## 6. Secondary objectives

To characterise and compare the pharmacokinetic profiles of the novel CBD formulation and a standard formulation

## 7. Secondary outcomes

Differences between novel and standard formulations for:

- i. Maximum plasma concentration ( $C_{max}$ )
- ii. Time after administration of drug when maximum plasma concentration is reached ( $T_{max}$ )
- iii. Plasma half-life ( $t^{1/2}$ )
- iv. Area under the concentration-time curve from time zero to 48hours ( $AUC_{0-48}$ )

## 8. Trial assessments

### 8.1. Blood sampling

Blood samples will be drawn at the following time-points on experimental visits:

Pre-dose (0-5mins), 0.5, 1, 2, 3, 4, 5, 6, 8, 24, and 48hrs post-dose. The 24hr and 48hour samples should be taken within 15minutes of the target time.

### 8.2. Vital signs

Vital signs (HR, RR, BP, Temp) will be recorded on experimental visits at the following times: pre-dose and 1, 2 4, 8, 24 and 48hrs post-dose. Urinalysis will be completed 4hrs post-dose. The 24hr and 48hour readings should be taken within 15minutes of the target time.

### 8.3. Adverse events

Participants will be asked to report adverse events at each blood sampling timepoint i.e. pre-dose (0-5mins), 0.5, 1, 2, 3, 4, 5, 6, 8, 24, 48hrs post-dose and at the 7-14 day follow-up visit . Participants will be asked specifically about adverse events including, but not limited to, anxiety, irritability, somnolence, dizziness, disorientation, nausea, abdominal pain, abdominal distension, diarrhoea, vomiting, and flatulence.

#### 8.4. Drug Effects Questionnaire (DEQ-5)

The DEQ-5 is questionnaire with five items, for example ‘‘Do you feel a drug effect, right now?’’ with the response anchors ‘Not at all’ and ‘Extremely’ (Morean et al. 2013). It will be recorded on experimental visits at the following times: pre dose and at 1, 2, 4, 8, 24 and 48hrs post-dose.

#### 8.5. Gastrointestinal Symptom Rating Scale (GSRS)

The GSRS is a 15-item rating scale which assesses five symptom clusters: reflux, abdominal pain, indigestion, diarrhoea and constipation. Each item is assessed with a 7-point Likert scale. The standard recall period for the scale is 7 days; this will be amended so that it assesses past 24 hours only. The scale will be used pre-dose and at 24 and 48 hours post dose.

#### 8.6. Stool Sample / Gut Microbiome (Exploratory analysis)

To assess the effect of the gut microbiome on the CBD’s pharmacokinetics and circulating endocannabinoid levels, a stool sample will be collected prior to each drug administration. Participants will be provided with stool sampling kits at the screening visit. This part of the study is optional.

### 9. Laboratory Analyses

Blood samples will be analysed for CBD and its metabolites (including 6-OH-CBD, 7-OH-CBD, 7-COOH-CBD) CBDA, THC, endocannabinoids (including anandamide and 2-arachidonoylglycerol). Additional unplanned analyses of relevant metabolites, biomarkers or inflammatory markers may also be completed. The laboratory analyses will be completed at the University of Turku, Finland. Analyses will be completed once all samples have been collected, at the end of the study. All analyses will be completed in accordance with relevant guidance and legislation.

## 10. Statistics and Data Analysis

### 10.1. Power analysis

As the means are unknown, we base the power calculation on minimum detectable difference assuming the AUC coefficient of variation in CBD is 50% (Taylor et al. 2018). Since there is no carry-over effect in the study, an appropriate analysis of continuous data from a two-period, two-intervention cross-over trial is a paired t-test. For the primary outcome, the bioavailability of lipid versus standard formulation in the fasted state, a paired t-test with n=12 has 80% power, at alpha=0.05 (2 tailed) to detect a 44.5% difference in means.

Previous studies demonstrated increased bioavailability with lipid formulations of 7x. The study is adequately powered to demonstrate these differences. This sample size and design satisfies EMA recommendations for design and minimum sample size (n=12) in pharmacokinetic studies for comparing formulations.

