10. STATISTICS AND DATA ANALYSIS

10.1 Power analysis

As the means are unknown, we base the power calculation on minimum detectable difference assuming the AUC coefficient of variation in CBD is 50% (Taylor et al. 2018(8)). Since there is no carry-over effect in the study, an appropriate analysis of continuous data from a two-period, two-intervention cross-over trial is a paired t-test (29). For the primary outcome, the bioavailability of lipid versus standard formulation in the fasted state, a paired t-test with n=12 has 80% power, at alpha=0.05 (2 tailed) to detect a 44.5% difference in means.

Previous studies demonstrated increased bioavailability with lipid formulations of 7x(19). The study is adequately powered to demonstrate these differences. This sample size and design satisfies EMA recommendations for design and minimum sample size (n=12) in pharmacokinetic studies for comparing formulations.

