10.3 Statistical analysis plan

Pharmacokinetics parameters

Pharmacokinetic parameters will be summarized descriptively. Continuous outcomes will be reported as means with standard deviation. Categorical outcomes will be reported as frequencies. Individual participant's pharmacokinetic data may also be presented in tables and graphs. The plasma concentration-time data will be subject to non-compartmental pharmacokinetic analysis using appropriate computer software applications. Linear and/or log-linear plots will be presented. To assess bioavailability between the formulations, log transformed AUC, C_{max} observations will be entered into a linear mixed model to account for the repeated measures and between subject conditions. Linear contrasts representing the difference between conditions will be expressed as ratio of geometric means along with 95% CI and inference based on $p < 0.05$. Planned analysis will be per protocol.

Protocol violations

All protocol violations, including inclusion/exclusion criteria violations and violations during the trial, will be listed, even if they are believed not to influence any of the results.

Demographics

For all participants, descriptive statistics of demographic (e.g., sex, age, BMI, and other baseline characteristics) will be presented by overall.

Safety measures

Summary tables showing vital signs e.g., body temperature, respiratory rate, pulse rate, and SBP and DBP will be provided at each study time point and changes from baseline.

Individual physical examination will be listed and summarised at each study time point. Important Medical Event, drug, pregnancy test results during the study will be listed.

Visual Analogue Scales & Drug Effects Questionnaire (DEQ-5)

A summary table of DEQ-5 will be summarised descriptively.

Laboratory results

Laboratory parameters including haematology, blood chemistry, and urinalysis will be listed accompanied by an indication if the parameter is outside the reference range. A summary of all data outside the reference range of the clinical laboratory will be provided. Clinical laboratory data will be presented descriptively, where applicable.

Adverse events

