### 10.6.6. Pharmacokinetics parameters

Pharmacokinetic parameters will be summarized descriptively. Continuous outcomes will be reported as means with standard deviation. Categorical outcomes will be reported as frequencies. Individual participant's pharmacokinetic data may also be presented in tables and graphs. The plasma concentration-time data will be subject to non-compartmental pharmacokinetic analysis using appropriate computer software applications. Linear and/or log-linear plots will be presented. To assess bioavailability between the formulations, log transformed AUC,  $C_{max}$  observations will be entered into a linear mixed model to account for the repeated measures and between subject conditions. Linear contrasts representing the difference between conditions will be expressed as ratio of geometric means along with 95% CI and inference based on  $p < 0.05$ . Planned analysis will be per protocol.

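### Is the stated 44.5% detectable difference the wrong power figure for a primary test run on log AUC?

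*SAP*

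**What the plan says.** The SAP (10.1) explains that, because the means are unknown, "we base the power calculation on minimum detectable difference". The input, also in protocol 10.1, is given as "assuming the AUC coefficient of variation in CBD is 50"%, with no statement of whether this is a per-formulation CV, a within-participant CV or the SD of the paired difference. No within-participant correlation is given. The output is that "a paired t-test with n=12 has 80% power, at alpha=0.05 (2 tailed) to detect a 44.5% difference in means". The section then compares this with the size of effect it expects: "Previous studies demonstrated increased bioavailability with lipid formulations of 7x".

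The analysis is described elsewhere. Protocol 10.3 and SAP 10.6.6 enter log-transformed AUC and Cmax into a linear mixed model, and "Linear contrasts representing the difference between conditions will be expressed as ratio of geometric means along with 95% CI". Neither document gives a detectable ratio of geometric means or an SD on the log scale.

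**The concern.** A power statement should describe the test that will be run. Here it is a difference in raw means from a paired t-test, while the primary result will be a ratio of geometric means from a log-scale model. A 44.5% difference and a ratio of 1.445 are not interchangeable: the same 50% CV can imply more or less than 80% power for that ratio, depending on what the CV describes. If the 50% were a within-participant CV, log-scale power at 1.445 would be only 41%. A reader could fairly ask whether n=12 has been justified for the primary analysis, and whether the quoted figure flatters the design.

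**Working it through.** **Inputs from the documents:** n=12 complete datasets (SAP 10.2); two-sided alpha 0.05, 80% power and a CV of 50% (SAP 10.1); expected effect 7-fold (SAP 10.1); other AUC gains with novel formulations, 2- to 3-fold and 7-fold (protocol section 3). **Not in the documents:** the type of CV and the within-participant correlation.

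**1. The plan's own figure.** For a paired t-test with n=12 (11 df), the non-central t distribution gives 80% power at a standardised difference of 0.8887.

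- If the SD of the paired difference is 50% of the mean: 0.8887 × 50% = 44.4%.
- Power at 44.5% exactly (0.445/0.50 = 0.89) is 80.1%.

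The figure reproduces. On the raw scale this reading is the same as a per-formulation CV of 50% with correlation 0.5, since 0.50 × √(2 × (1 − 0.5)) = 0.50. If 50% were instead the within-participant CV, the SD of the difference would be 0.50 × √2 = 0.707, and raw-scale power at 44.5% would be 51%. That is not the calculation that was done.

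**2. Is the test itself different?** SAP 10.3.2 restricts the per-protocol set to participants who completed both visits. With complete pairs, a mixed model with participant and formulation effects is in essence a paired t-test on the logs. Only the scale differs. If a period term is added (10 df, an assumption), the required standardised difference becomes 0.8978, which is a trivial change.

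**3. Log scale.** A CV of 50% corresponds to σ = √ln(1 + 0.5²) = 0.472. The detectable ratio is exp(0.8887 × SD of the log difference). The correlations below are assumptions.

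| Reading of the 50% | SD of log difference | Detectable ratio | Power at 1.445 | Power at 2 |
|---|---|---|---|---|
| Within-participant CV | 0.472 × √2 = 0.668 | 1.81 | 41% | 90% |
| Per formulation, log correlation 0.3 | 0.559 | 1.64 | 55% | 97% |
| SD of the difference, taken as 0.50 on the log scale | 0.500 | 1.56 | 64% | 99% |
| Per formulation, log correlation 0.5 | 0.472 | 1.52 | 69% | >99% |
| Per formulation, raw correlation 0.5 (log correlation ln 1.125 / ln 1.25 = 0.528) | 0.459 | 1.50 | 72% | >99% |
| Per formulation, log correlation 0.7 | 0.366 | 1.38 | 89% | >99% |
| Per formulation, log correlation 0.8 | 0.299 | 1.30 | 97% | >99% |

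For a 7-fold ratio the standardised effect is at least ln 7 / 0.668 = 2.91, and power exceeds 99.9% in every row.

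**4. Does the quoted effect fall short of 80% on the log scale?** Keep only readings that reproduce 44.5%.

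- Percentage of the reference mean (ratio 1.445), SD of log difference 0.46 to 0.50: power 72% down to 64%.
- Percentage of the average of the two means: ratio (1 + 0.2225)/(1 − 0.2225) = 1.57, ln 1.57 = 0.453. Over the same SDs, power is 87% down to 81%.
- SD of the raw paired difference equal to 50% of the reference mean when the true ratio is 1.445, with lognormal data and a 50% CV for each formulation. Then 0.25 × (1 + 1.445²) − 2 × 1.445 × (exp(ρσ²) − 1) = 0.25, which gives ρ = 0.744. The SD of the log difference is 0.472 × √(2 × 0.256) = 0.338, and power is 93%.

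The answer lies on either side of 80% according to conventions that the text leaves open.

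**5. A rough check on paired variability.** Protocol section 3 quotes, from the study that supplied the CV, a fed-to-fasted AUC ratio of 4.2 (90% CI 3.63 to 4.85). If that comparison was paired with n participants (design and n are assumptions), the SD of the log difference is ln(4.85/3.63) × √n / (2 × t), with t the 95th percentile on n − 1 df. This gives 0.28 at n=12, 0.41 at n=24 and 0.54 at n=40, hence detectable ratios of 1.28, 1.44 and 1.62. It is a food comparison and so only indirect. The 0.668 of the least favourable row would need about 60 participants.

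**The case for a change.** The best argument for a change is that the plan chose the minimum detectable difference as its basis precisely because the means are unknown. Having done so, it should state that difference for the primary analysis and define its variability input. The 7-fold figure comes from a pilot of another lipid formulation at 10 mg, so a smaller effect is possible, and that is where a detectable ratio would inform the reader. The SAP has still to be finalised before database lock, and the edit would take one paragraph.

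Part of this stands. The CV type is undefined, the scale conversion is missing, and naming both would make 10.1 clearer. It does not amount to a defect in the plan. The smallest AUC gain the protocol cites for a novel formulation, 2- to 3-fold, has at least 90% power at its lower end under every row of the table. A replacement figure would need either a CV type that the documents do not give or a set of correlations chosen by the reviewer (0.9 instead of 0.8 would take the lower end from 1.30 to 1.21). It would exchange one unexplained number for several assumed ones. Once the trial reports, the 95% CI for the ratio shows directly what the data exclude, whatever 10.1 says.

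**Conclusion.** No change is needed. The 44.5% is a correct paired t-test result when 50% of the mean is the SD of the paired difference. That reading corresponds to a detectable ratio of geometric means of about 1.50 to 1.56, if the SD is carried to the log scale as 0.46 to 0.50. The documents do not settle whether 44.5% is optimistic or conservative for the log-scale test: readings consistent with the figure give power from 64% to 93%. Across the wider range of assumptions (within-participant CV of 50%, or per-formulation CV of 50% with correlation 0.3 to 0.8), the detectable ratio runs from 1.30 to 1.81, well below 2-fold and far below 7-fold. The conclusion that the study is adequately powered, the requirement for 12 complete datasets and the planned log-scale analysis are unaffected. What is left is a gap in explanation that a statistician can fill from the figures given, and filling it would alter no decision and no reported result.

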### 10.2. Planned recruitment

The study requires 12 complete datasets. With an expected drop-out rate of 15%, we expect to recruit 14 participants.

### 10.3. Analysis populations

#### 10.3.1. Full Analysis Set (FAS)

The FAS will consist of all randomized/assigned participants who had at least one dose of treatment. FAS participants are analysed according to their randomized/assigned treatment.

### 10.3.2. Per Protocol Population Set (PPS) or PK analysis population

The PPS will consist of all participants with completed two experimental visits and have a measurable level for all timepoints.

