6.2 Exclusion criteria

- i. Clinically relevant medical history, physical findings, ECG, or laboratory values at the pre-trial screening assessment that could interfere with the objectives of the trial or the safety of the participant.
- ii. Presence of acute or chronic illness or history of chronic illness sufficient to invalidate the volunteer's participation in the trial or make it unnecessarily hazardous.
- iii. Impaired endocrine, thyroid, hepatic, respiratory or renal function, diabetes mellitus, coronary heart disease, or history of any neurological or mental illness.
- iv. Surgery or medical condition that might affect absorption of medicines.
- v. Blood pressure and heart rate in supine position at the screening examination outside the ranges: blood pressure 90–140 mm Hg systolic, 40–90 mm Hg diastolic; heart rate 40–100 beats/min. Repeat measurements are permitted if values are borderline (i.e. values that are within 5 mm Hg for blood pressure or 5 beats/min for heart rate) or if requested by the investigator. Subjects can be included if the repeat value is within range or still borderline but deemed not clinically significant by the investigator.
- vi. Loss of more than 400 mL blood during the 3 months before the trial, e.g. as a blood donor.
- vii. Any prescribed medication (apart from contraceptives)
- viii. Use of any CBD products within six months of IMP administration
- ix. Use of any over-the-counter medications or health supplements within the past 2 weeks
- x. $BMI <18$ or $>30.0\text{kg}/\text{m}^2$
- xi. History of alcohol or substance misuse disorder
- xii. Intake of more than 14 units of alcohol weekly.
- xiii. Smokes more than 10 cigarettes per day
- xiv. Use of any illicit substances within the last six months
- xv. Pregnant or breastfeeding
- xvi. Women of childbearing potential (as defined in CTFG guidelines, see 5.7 Concomitant Medication) not willing to use a highly effective form of contraception (as defined in CTFG guidelines, see section 5.7 Concomitant Medication) during participation in the study or male patients not willing to ensure use of a condom during participation in the study.
- xvii. $eGFR \leq 70 \text{ mls}/\text{min}$
- xviii. Any liver function or renal function test abnormality. A repeat is allowed on one occasion for determination of eligibility.
- xix. Urine drug screen positive for any substances
- xx. Positive alcohol breath test

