### 10.4.2. PK time points windows

The target sampling days and times with windows for PK samples in Experimental visit 1 and 2 are shown in below table. In the event of repeat values within a window, the last non-missing value per study day/time will be used.

Target Day of Visit	Timepoints with window
Day 1	Pre-dose (0-5mins) 0.5-hour (post dose) +/- 5 mins 1-hour (post dose) +/- 5 mins 2-hours (post dose) +/- 5 mins 3-hours (post dose) +/- 5 mins 4-hours (post dose) +/- 5 mins 5-hours (post dose) +/- 5 mins 6-hours (post dose) +/- 5 mins 8-hours (post dose) +/- 5 mins
Day 2	24-hours (post dose) +/- 5 mins
Day 3	48-hours (post dose) +/- 5 mins

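### As written, no valid participant can enter the set used for the primary AUCinf comparison, because it requires a measurable level before the first dose

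*SAP*

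**What the plan says.** SAP 10.3.2 treats the per-protocol set and the PK analysis population as one set and defines it in a single sentence: "The PPS will consist of all participants with completed two experimental visits and have a measurable level for all timepoints". SAP 8.1 lists the sampling timepoints as "Pre-dose (0-5mins), 0.5, 1, 2, 3, 4, 5, 6, 8, 24, and 48hrs post-dose". The PK window table in SAP 10.4.2, which covers both experimental visits, also opens with pre-dose: "Pre-dose (0-5mins) 0.5-hour (post dose) +/- 5 mins". For the log-transformed AUC and Cmax model, SAP 10.6.6 states: "Planned analysis will be per protocol". A full analysis set is defined in SAP 10.3.1 but is not assigned to the PK comparison.

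Protocol 6.2 (viii) excludes "Use of any CBD products within six months of IMP administration". SAP 10.4.3 says that missing data will not be imputed. Neither document defines measurable, gives a quantification limit, or says how levels below it are handled.

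**The concern.** The inclusion rule conflicts with the eligibility criteria. The only participants who could satisfy it at visit 1 are those with undeclared CBD exposure or assay background. The primary comparison therefore cannot be run on its stated population without an unplanned change.

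The timing adds to this. For the laboratory work, SAP 9 says: "Analyses will be completed once all samples have been collected, at the end of the study". Protocol 6.9 places unblinding at the end of data collection, and the final SAP is due only before database lock. A repair could thus be chosen when concentrations, and possibly allocation, are already known.

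Waiving pre-dose leaves a second problem. The set would still be selected on the concentrations from which AUC is calculated, and with 12 planned completers each exclusion counts. Replacement under Protocol 6.10 covers people who withdraw. It does not cover those removed later because a level was unmeasurable.

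**Working it through.** **The plan's own figure.** SAP 10.1 assumes a 50% CV and states that 12 participants give 80% power at two-sided 0.05 for a 44.5% difference. Taking the 50% as the SD of the paired difference, the standardised effect is 0.445/0.5 = 0.89. The exact noncentral-t power at n = 12 is 0.801, and the detectable difference at 80% power is 44.4%. The stated figure reproduces.

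**Step 1: the literal rule.**
- Timepoints: pre-dose plus 10 post-dose per visit, so 11 × 2 = 22 per participant, all of which must be measurable.
- Visit 1 pre-dose: a participant who meets exclusion viii has no measurable CBD.
- Carry-over cannot rescue the rule. It could affect only visit 2, and the plan assumes none ("Since there is no carry-over effect in the study", SAP 10.1).
- Result: 0 of 14 recruited, or 0 of 12 completers.

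**Step 2: ignoring pre-dose.** A participant now needs all 10 × 2 = 20 post-dose levels. If k samples are at risk and each fails independently with probability q, the share lost is 1 − (1 − q)^k. The values of q and k are assumptions, since the documents give none.

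| Samples at risk | q | Share lost | 12 become |
|---|---|---|---|
| none | – | 0% | 12 |
| 0.5 h only, k = 2 | 5% | 9.75% | 10.8 |
| 0.5 h and 48 h, k = 4 | 5% | 18.5% | 9.8 |
| all, k = 20 | 1% | 18.2% | 9.8 |
| all, k = 20 | 2% | 33.2% | 8.0 |
| all, k = 20 | 5% | 64.2% | 4.3 |

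The k = 20 rows are upper illustrations. Failures that cluster within people would lower these losses.

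**Step 3: selection on the outcome.** The log SD implied by a 50% CV is √ln(1 + 0.5²) = 0.472. Suppose a share f is dropped for a low level on one formulation. Let g be the correlation of that level with the same formulation's log AUC, and ρ the correlation of log AUC between formulations. The SEEK/STD ratio is then multiplied by exp(∓0.472 · g · m · (1 − ρ)), with m = φ(a)/(1 − f) and a the f-quantile of the standard normal. The sign is minus if people are dropped for low STD-CBD levels and plus if dropped for low SEEK-CBD levels.
- Assumed ranges: f 0.10–0.40, g 0.3–0.9, ρ 0.3–0.7.
- Central case (f = 0.25, g = 0.6, ρ = 0.5): m = 0.318/0.75 = 0.424, and the exponent is 0.472 × 0.6 × 0.424 × 0.5 = 0.060. The factor is 0.942 or 1.062; a simulation of 1,000,000 gave 0.942 and 1.061.
- Full range: 0.826–0.992 (low on STD-CBD) or 1.008–1.211 (low on SEEK-CBD). A true ratio of 7 would read as about 5.8–6.9 or 7.1–8.5.

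The direction is open. Low levels might be expected on the standard formulation, but Protocol 3 says the novel one is designed for absorption in the ileum, so low early levels could occur there too.

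**Step 4: power.** For a true ratio of 7 (paired t on logs), power exceeds 0.999 at n = 8. At n = 4 it is 0.999 with a difference SD of 0.472, and 0.959 with 0.668 (0.472 × √2, uncorrelated formulations). At the plan's own 44.5% difference it falls from 0.801 (n = 12) to 0.708 (n = 10) and 0.582 (n = 8).

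**The case against.** The strongest reply is that the authors meant a sample obtained and assayed at every timepoint. SAP 10.2 supports this ("The study requires 12 complete datasets"), and under that reading the set is not empty. The reading is plausible, but 10.3.2 makes the level itself the condition, and nothing in the SAP tells an analyst to read it otherwise.

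A second reply is that the later figures have no documentary basis. This is correct: q, f, g and ρ are all assumed, and the loss may be zero. The extremes of 0.83 and 1.21 need f = 0.40, g = 0.9 and ρ = 0.3 together. With 10% dropped, the same formula gives 0.944–0.992, so 7 would read about 6.6–6.9, or 7.1–7.4 in the other direction. Independent random failures cause loss without selection, so the largest losses in step 2 and the largest biases in step 3 should not be combined. Exclusions on both formulations would partly cancel.

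Third, some missing samples are already covered. Protocol 6.10 (vii) makes failure to attend a follow-up point a withdrawal criterion, and withdrawn participants are replaced. A missed 24 h or 48 h attendance may fall under this. Below-quantification levels and failed in-clinic or laboratory samples do not.

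Finally, a 7-fold effect would be detected under any of these scenarios. That stands, but the trial also aims to characterise and compare the two profiles, so the size of the ratio matters as well as its significance.

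**Conclusion.** The concern holds and must be fixed. The set specified for the primary AUCinf analysis contains 0 of 14 valid participants when the rule is applied as written. This follows from the documents alone, provided that a person with no CBD use for six months has no measurable pre-dose level.

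If pre-dose is disregarded, the set remains dependent on the outcome. The amount lost and the size and direction of any bias rest on an unstated quantification limit, so the figures above are illustrations and not forecasts. The finding that the novel formulation raises exposure is not threatened if the effect is near 7-fold. What is at risk is the pre-specification of the primary analysis and the accuracy of the estimated ratio.

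**What to change.** Reword SAP 10.3.2 before unblinding (Protocol 6.9), not merely before database lock:

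1. Define the PK set as participants who received both formulations at the same dose and have enough post-dose samples drawn and assayed in each period to derive the parameter. Fix the minimum number in advance, and base it on samples obtained, not on whether levels are low.
2. Exempt pre-dose from the requirement.
3. Set below-quantification levels before the first measurable sample to zero.
4. State the rule for later below-quantification levels and for isolated missing samples separately for AUCinf and AUC0-48. Ending at the last measurable level does not by itself give AUC0-48.
5. Report participants whose AUCinf cannot be extrapolated, and keep them in the AUC0-48 comparison.

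Two additions would be useful. The pre-dose level can serve as a carry-over check against a threshold that the sponsor sets in advance. The primary comparison can also be repeated in all full-analysis-set participants with estimable parameters, as a sensitivity analysis.

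The cost is SAP wording and one sensitivity table. No new data are needed.
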